### Fracture Healing

Radiographic union will be measured by evidence of fracture healing defined by the Radiographic Union Scale in Tibial fractures (RUST) score, Clinical union will be defined by: 1. Pain free full weight bearing and/or 2. The absence of pain to palpation at the fracture site.

Clinical Success will be determined by the clinical investigators on the basis of both:

1. Radiographic evaluation will be assessed by blinded orthopaedic surgeons and will use consensus adjudication to determine union measured by the RUST score.

2. Clinical healing is defined as pain free, full unsupported weight bearing and lack of tenderness at the fracture site on palpation. The fracture will be considered to be a Clinical Success (e.g. healed) when radiographic union is confirmed and both clinical parameters listed above for healing has been met.

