**A. INVESTIGATIONAL PLAN**

**Purpose**

Fractures of long bones constitute the majority of emergency operating room procedures in most trauma centers. Of these long bone injuries, tibial fractures are the most common. The National Center for Health Statistics reports an annual incidence of 492,000 fractures of the tibia and fibula per year in the United States. Patients with tibial fractures remain in the hospital for a total of 569,000 hospital days and incur 825,000 physician visits per year in the United States. Delayed fracture healing is a common complication associated with high-energy tibia fractures. Open tibia fractures with bone loss rarely unite without a secondary intervention. Delayed bone grafting of the defect is commonly used to provide stimulus for healing. The use of an autogenous iliac crest bone graft (ICBG) has remained the gold standard in the treatment of tibial non-unions with a bone defect. However, there are significant limitations to autogenous bone grafting, including the increased risk of infection from a second surgical incision and pain associated with the bone graft harvest site, which may range from 1-5 days to more than a year. Additional risks include iatrogenic fracture and damage to neurovascular structures. Also, not all patients are suitable donors. Relative contraindications to ICBGs include previous iliac crest harvesting; poor bone quality secondary to underlying disease, smoking or medications that affect the quality of bone; and advanced patient age. Finally, there is a finite amount of bone that may be obtained from the ilium, and it may not be adequate in all donors to address critical size defects. Recent technological advances with the advent of recombinant bone morphogenetic proteins emerging as a viable bone graft substitute may offer a viable alternative for patients.

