## **IRB00003098 Funding Protocol rhBMP-2/ACS vs. Autograft for Critical Size Tibial Defects**

*Null hypothesis: rhBMP-2/ACS has the same union rate when used in critical-sized defects as does ICBG.*

*Secondary:*

What is the relative effect of rhBMP-2 versus autogenous ICBG on infection rates in patients with nonunion or critical size defects following tibial shaft fractures?

*Null hypothesis #2: The infection rate in open tibias with critical-sized defects treated with rhBMP-2 and autogenous ICBG are the same.*

What is the economic impact of the use of RhBMP 2 for tibial fractures with critical sized defects?

*Null hypothesis #3: There will be no difference in the economic cost of the treatment of critical sized defects using the RhBMP-2 versus iliac crest bone graft.*

This investigation is a prospective, stratified, parallel, randomized, blinded multicenter trial to evaluate the use of rhBMP-2/ACS in 25 patients versus a control group of 25 patients who have tibial fractures with critical size defects. A committee of orthopaedic surgeons will independently adjudicate our primary outcome, fracture healing at 12 months. Participating centers are part of the Major Extremity Research Consortium (METRC) and have experience with performing randomized clinical trials. Approval by each center's institutional review board will be obtained prior to commencing the study and we will follow the research guidelines set forth by each site.

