#### Risks Associated with Standard Treatment

The risk of standard treatment with iliac crest bone graft harvest includes infection, bleeding, donor site pain, and possible increased length of hospital stay.

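### The rule for calling a fracture healed asks for pain-free weight bearing without saying where the pain is, so iliac-crest donor-site pain can fail a united control tibia

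*Combined protocol and SAP*

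**What the plan says.** Fracture Healing contains two clinical definitions.

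- Clinical union is "1. Pain free full weight bearing and/or 2. The absence of pain to palpation at the fracture site".
- The Clinical Success rule is stricter. It states "Clinical healing is defined as pain free, full unsupported weight bearing and lack of tenderness at the fracture site on palpation", and counts a fracture as healed "when radiographic union is confirmed and both clinical parameters listed above for healing has been met".

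In both, the site is attached to palpation, and the pain on weight bearing has none.

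On who decides, the same section says "Clinical Success will be determined by the clinical investigators on the basis of both" a radiographic part, read by blinded surgeons using RUST, and a clinical part. The design paragraph after the hypotheses says "A committee of orthopaedic surgeons will independently adjudicate our primary outcome, fracture healing at 12 months".

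On donor-site pain, Purpose refers to "pain associated with the bone graft harvest site, which may range from 1-5 days to more than a year". Risks Associated with Standard Treatment lists "infection, bleeding, donor site pain, and possible increased length of hospital stay". Under Surgical Treatment, controls receive iliac-crest autograft and the investigational arm receives rhBMP-2 with allograft, which needs no harvest. Measurements has pain scored by VAS at every visit and gives no body site for the score.

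**The concern.** An outcome meant to describe the tibia can be failed by pain from the pelvis. Among the assigned treatments, only the control procedure creates that pain. A literal assessor would lower the observed control healing rate for a reason unrelated to union, which makes rhBMP-2 look better than it is.

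The direction matters because Sample Size Justification is framed as non-inferiority. Lowering the observed control rate makes a worse graft easier to accept. Blinded reading of the radiographs does not remove the problem, because the composite also requires the clinical part. With up to 22 sites, the choice between a literal and a fracture-only reading is left to each assessor. The plan describes no pain-site data from which the effect could be undone at analysis.

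**Working it through.** **Inputs from the plan (Sample Size Justification).** Control healing 65%; rhBMP-2 healing 20 points higher, so 85%; power 80%; alpha 0.05; margins of 20 and 10 points; 25 patients per arm.

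**The plan's own figure.** With one-sided alpha 0.05, n per arm = (1.645 + 0.842)² × (0.65×0.35 + 0.85×0.15) / (0.20 + margin)².
- The numerator is 6.18 × 0.355 = 2.195.
- 20-point margin: 2.195 / 0.16 = 13.7, so 14.
- 10-point margin: 2.195 / 0.09 = 24.4, so 25.

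Both stated figures reproduce. This point does not dispute them.

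**Does the text allow the failure?**
1. Healed requires radiographic union and both clinical parameters.
2. One parameter is weight bearing without pain, with no site given.
3. Donor-site pain may last beyond a year, so it can be present at the 12-month assessment.
4. The control arm has a donor site by assignment and the rhBMP-2 arm does not.

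Each step is documented. The frequency is not.

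**Illustrative size.** Let d be the share of truly healed controls who are failed for donor-site pain alone. The documents give no value, so the values below are assumptions. Take 65% as the rate before any such failures.
- Observed control rate = 65% × (1 − d).
- Shift towards rhBMP-2 = 65% × d.
- Expected healed controls = 25 × 0.65 = 16.25.

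| d | Observed control rate | Shift (points) | Controls reclassified (16.25 × d) |
|---|---|---|---|
| 5% | 61.8% | 3.3 | 0.8 |
| 10% | 58.5% | 6.5 | 1.6 |
| 20% | 52.0% | 13.0 | 3.3 |

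**Effect on error rates, 25 per arm.** Two readings of the analysis are possible.

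- *Non-inferiority, 10-point margin, one-sided 0.05.* Take rhBMP-2 as truly 10 points worse (55% against 65%). The chance of declaring non-inferiority is Φ[(0.10 − (pc − 0.55))/SE − 1.645], where pc is the observed control rate and SE = √{[pc(1 − pc) + 0.55×0.45]/25}. It is 5.0% at d = 0, and 7.9%, 11.9% and 23.5% at d = 5%, 10% and 20%. Exact binomial enumeration gives 7.8%, 11.5% and 22.5% for the three non-zero values.
- *Fisher's exact test, two-sided 0.05, true healing 65% in both arms.* The chance of a significant result favouring rhBMP-2 is 1.3% at d = 0, and 2.4%, 4.3% and 10.9% at d = 5%, 10% and 20%.

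**The case against.** Five counter-arguments deserve weight.

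- **Investigators may read the criterion as fracture pain.** Steps to Minimize Risk lists pain within the physical evaluation of the limb, and the criterion sits under a fracture-healing heading. That reading is reasonable. A reader might infer that a site is compelled to fail any control with pelvic pain, but the text permits that result and does not force it. Even so, the limb passage does not define the outcome.
- **The looser definition escapes the problem.** Its and/or lets a non-tender tibia meet clinical union despite donor-site pain. This stands. The fault lies in the Clinical Success rule, which needs both parameters.
- **The primary outcome may be radiographic union.** The research question speaks of union rates, the committee's described task is RUST reading, and Measurements lists radiographic and clinical union separately. No section says that Clinical Success is primary. This also stands, and it makes the effect on the primary outcome conditional.
- **The rhBMP-2 arm is not immune.** A reader might infer that this failure is impossible there. The inclusion criteria allow bilateral fractures with each tibia randomised separately, so a patient with one tibia in each arm has a donor site. Retrieval Study provides for salvage autograft after failed rhBMP-2. Both routes are exceptions, so almost only the control arm is the accurate wording.
- **The size has no anchor.** Purpose gives a range of durations, with no frequency at 12 months and nothing on weight bearing. Risks Associated with Both Treatments says the injury itself causes pain whatever the treatment, so unlocalised pain can fail patients in either arm. Only controls who are united, non-tender and otherwise pain free count towards d. Final Analysis names Fisher's test and no non-inferiority test. Under Fisher, d = 5% gives 2.4%, still inside the nominal 2.5% tail.

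**Conclusion.** The point holds as a fault in the outcome wording. Applied literally, the Clinical Success rule can record a united, non-tender control tibia as not healed because of donor-site pain, and the resulting bias favours rhBMP-2. It touches the primary comparison only if the 12-month outcome is the composite. Otherwise it is confined to Clinical Success.

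The shifts of 3.3, 6.5 and 13 points rest on assumed d values and the plan's 65%. The non-inferiority error rates also assume a one-sided 0.05 test that Final Analysis does not specify. A reader might infer that the bias is large enough to use up the 10-point margin. That would need d = 10/65 = 15.4%, or about 2.5 of 16.25 healed controls, and the documents neither support nor exclude such a share.

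This should be fixed because the fix is cheap. The documents do not show that the trial's conclusion depends on it.

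**What to change.** In Fracture Healing:

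1. Word the weight-bearing criterion as full, unsupported weight bearing without pain at the tibial fracture site.
2. State that pain at the iliac crest or from other injuries does not count against fracture healing and is recorded separately.
3. Reconcile the and/or in clinical union with the requirement for both parameters in Clinical Success.
4. State which definition is the 12-month primary outcome that the committee adjudicates.

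Also make sure the follow-up case report form records the site of any pain on weight bearing. The form is not among the documents, so it may already do so.

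The cost is a few sentences and at most one form item. The assessor has to ask where the pain is. The stated sample size is unchanged, and donor-site pain is still captured as an outcome in its own right.

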### Final Analysis

The results will be reported comparing the outcomes in the groups at each follow-up period. It is anticipated that the required patients will be entered into the investigation during an 18-month period and will be followed for one year. Thus, the data collection time will be a 2.5- year period. We believe that at that time, the results of the study will reveal whether any differences exist with this high-energy disabling fracture in terms of outcomes, union rates, times to union, soft-tissue complications and infection rates.

Data will be analyzed on an intent to treat basis (patient data included in the treatment group and stratum to which randomized). Fishers exact test will be used to compare categorical variable and the Student t test will be used for continuous variables for comparisons between the two groups.

Quality of life data will be coded and scored according to the guidelines provided with the SMFA (Coding Key Manual, Musculoskeletal Function Assessment, Injury and Arthritis Survey) and the SF-12 (Coding Manual for the SF-12 Health Survey).

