### Steps to Minimize Risk

There may be unknown risks/discomforts involved. Study staff will update the participant's in a timely way on any new information that may affect the patient's health, welfare, or decision to stay in this study. The risks of participation in this study if one is randomized to the Rh-BMP 2 group are documented from previous studies. If there is an accelerated healing rate in those patients who receive rhBMP-2 versus the autograft, the patient benefits may include less pain, a decrease in the need for secondary interventions, and improved functional outcome. If there is no healing with the use of the Rh-BMP 2 group, the patient will still be able to receive autograft to promote healing.

The patient's physician and the study investigators will share responsibility for patient safety. They will ensure patient confidentiality throughout trial management. The investigator and designated study staff will be responsible for adhering to institutional standards for ensuring patient safety and confidentiality.

At each clinical visit, assessment will be made based on vital signs, physical evaluation of the limb including skin inspection, pain, swelling, infection, neurovascular status and radiographic evaluation of the involved tibia. There will be close monitoring of the occurrences of adverse events. In addition, certain vulnerable patient populations have been excluded from this study.

Every effort will be made to keep patient information confidential.

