### Retrieval Study

Should a patient fail to heal with the use of Bone Morphogenetic protein-2, salvage would be attempt of autogenous bone graft. As the sponge is dissolved within 14 days and the product thus would not be retrievable at salvage surgery.

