### **Monitoring Procedures**

This study is being conducted under the umbrella of the Major Extremity Trauma Research Consortium (METRC). The Consortium has developed an independent Data Safety Monitoring Board (DSMB) charged with the task of safety monitoring of all Consortium studies.

At its first meeting the DSMB will review definition of all outcomes, adverse events and serious adverse events and revisions to the protocol will be made as appropriate. Summary data on adverse events (together with study outcomes) will be monitored by the DSMB at its semiannual meetings or more frequently, as needed. These summaries will include analyses comparing rates of adverse events by blinded treatment group, by clinic, or in other subgroups requested by the DSMB.

After each meeting, the DSMB will issue a written summary of its review of the study data, including adverse events, for transmission to the IRBs at Johns Hopkins Bloomberg School of Public Health and each of the study centers.

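### The 12-month union endpoint does not say how a re-graft counts, so a first-graft failure united by a second graft can score as a success of the randomized graft

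*Combined protocol and SAP*

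**What the plan says.** - **Primary outcome.** After the null hypotheses, the protocol has a committee of orthopaedic surgeons "independently adjudicate our primary outcome, fracture healing at 12 months".
- **Healing rule.** Under Fracture Healing, "The fracture will be considered to be a Clinical Success (e.g. healed) when radiographic union is confirmed" and the two clinical criteria (weight bearing without pain or support, and no tenderness at the fracture) are met. Nothing there refers to procedures after the index graft. The same section says "Clinical Success will be determined by the clinical investigators", with blinded surgeons reading the radiographs.
- **Salvage.** Under Retrieval Study: "Should a patient fail to heal with the use of Bone Morphogenetic protein-2, salvage would be attempt of autogenous bone graft". Steps to Minimize Risk adds that, without healing after rhBMP-2, "the patient will still be able to receive autograft to promote healing". Re-grafting of a control patient is neither described nor ruled out.
- **Analysis.** Under Final Analysis, "Data will be analyzed on an intent to treat basis", and Fisher's exact test is named for categorical outcomes. Also: "The results will be reported comparing the outcomes in the groups at each follow-up period".
- **Related provisions.** Measurements lists second procedures under effectiveness and has a separate outcome for further intervention. Monitoring Procedures provides, for the board's opening session, that "the DSMB will review definition of all outcomes, adverse events and serious adverse events and revisions to the protocol will be made as appropriate".

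**The concern.** The primary research question asks for the relative effect of the two grafts on union. An rhBMP-2 failure that then unites after autograft has been healed by the comparator. If that patient is scored as healed at month 12 and kept in the rhBMP-2 arm, the union is credited to rhBMP-2. The same applies to a control patient who needs a second graft.

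Two things are at stake. First, rescue pulls the arms together: it masks a real deficit of rhBMP-2 and also hides a real advantage. Second, two careful adjudicators could score the same patient differently. With 25 per arm, one patient moves an arm's rate by 1/25 = 4 points, against a 10-point non-inferiority margin.

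**Working it through.** **1. What the text determines.** Intent to treat fixes the arm a patient is counted in, not whether the fracture counts as healed. The healing rule, read alone, is met by a re-grafted fracture that unites by month 12. Two links are weaker. The plan never says that Clinical Success is the committee's primary outcome, and it gives the two determinations to different people. The Retrieval Study wording describes the salvaged patient as one in whom rhBMP-2 failed, which an adjudicator could take as a failure. So both scores can be defended.

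**2. Reproducing the sample size.** From Sample Size Justification: control 65%, rhBMP-2 85% (20% higher, read as absolute), power 80%, alpha 0.05. With unpooled variance and a one-sided test:

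n = (1.645 + 0.842)² × (0.65×0.35 + 0.85×0.15) / (0.20 + margin)²

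- Margin 0.10: 6.183 × 0.355 / 0.09 = 24.4, so 25 per arm.
- Margin 0.20: 6.183 × 0.355 / 0.16 = 13.7, so 14 per arm.

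Both match the plan. One-sided 0.025 would give 31 and 18, so one-sided 0.05 is used below.

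**3. Effect of rescue.** Let r be the share of first-graft failures that are re-grafted and meet the healing rule by month 12. The observed rate is p + r(1 − p). With the same r in both arms, the observed difference is (1 − r) times the true one. A 10-point deficit reads as 8 or 6 points at r = 20% or 40%; a 20-point advantage reads as 16 or 12.

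Observed rates at r = 0 / 20% / 40%:
- from 55%: 55 / 64 / 73%
- from 65%: 65 / 72 / 79%
- from 85%: 85 / 88 / 91%

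**4. Consequence for the conclusion.** Exact binomial enumeration, 25 per arm. The non-inferiority test is Farrington-Manning, margin 0.10, one-sided 0.05 (assumed, since the plan names no non-inferiority test). Fisher's test is two-sided 0.05 (sidedness assumed).

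| First-graft rates (rhBMP-2 v control) | Result | r = 0 | r = 20% | r = 40% |
|---|---|---|---|---|
| 55% v 65% | Non-inferiority declared | 4.5% | 6.8% | 10.0% |
| 85% v 65% | Non-inferiority declared | 80.7% | 76.1% | 71.5% |
| 85% v 65% | Fisher shows rhBMP-2 better | 25.3% | 18.8% | 12.1% |

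Under the stated null of equal union rates, equal rescue leaves the arms equal. Fisher's test then loses power but gains no false difference.

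**5. How plausible is r?** The documents give no rescue rate and no timing of salvage. At the design rates, r = 20% is 25 × 0.15 × 0.20 = 0.75 rhBMP-2 patients and 25 × 0.35 × 0.20 = 1.75 controls. If a re-graft unites at the plan's 65% (an assumption), r = 20% or 40% means re-grafting 0.20/0.65 = 31% or 0.40/0.65 = 62% of failures. So 40% is a high value.

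**6. Unequal rescue.** The arm rescued more often gains. At 55% v 65%, the chance of declaring non-inferiority is 22.5% with 40% rescue for rhBMP-2 and 20% for control, and 2.2% with these reversed.

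**The case against.** **The plan leaves the score open; it does not fix a wrong one.** This stands. A reader might infer that re-grafted rhBMP-2 patients will definitely be counted as rhBMP-2 successes, or that the design is tilted toward rhBMP-2 because salvage is described only for that arm. The documents support neither. The link from the healing rule to the primary outcome is inferred, the Retrieval Study wording allows a failure score, and nothing denies controls a second graft. Equal rescue is not documented either, so the direction of any bias is unknown.

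**The raised error rate needs a test that Final Analysis does not name.** This also stands. The non-inferiority figures borrow the framework of the sample size section. Under the named Fisher test, equal rescue only costs power.

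**Union regardless of later procedures is a recognised treatment-strategy question and fits intent to treat.** True, and the research question does not strictly exclude it. But the plan does not say that it chose this question, and here the rescue in one arm is the comparator itself.

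**Counting a re-graft as failure brings a decision by surgeons who know the arm into the endpoint.** This is a real cost. One extra failure in 25 in the rhBMP-2 arm alone (81% v 65%) lowers power from 80.7% to 67.7%, more than 40% equal rescue does. It is the reason to report both analyses.

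**Safeguards already exist.** Further intervention is an outcome, results are reported by visit, and the DSMB reviews outcome definitions. These would show re-grafts and offer a route to amend, but none ties a re-graft to the union score. Some text near the monitoring and reporting sections was not available to check.

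**Conclusion.** The point holds as a gap in the definition of the primary endpoint, and it should be closed. That no available text says how a re-graft counts toward 12-month union is plain. That the literal rule credits the randomized graft with a union achieved by a second graft follows only if the Fracture Healing section defines the primary outcome. The firm conclusion is that the primary result can depend on how an adjudicator reads the plan.

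The size is uncertain. The factor 1 − r needs only equal rescue in both arms. The probabilities also rest on assumed values of r and, for non-inferiority, on an assumed test. At r = 20% they are modest: 2.3 points more chance of a wrong non-inferiority claim at the margin, and 4.6 points less power in the design case. They should be read as illustration, not as the trial's actual error rates.

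**What to change.** This changes scoring only, not care. Before the interim evaluation at 25 enrolled:

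1. State under Fracture Healing that the section defines the adjudicated 12-month primary outcome. Add that, in both arms alike, a fracture re-grafted to promote union after the index graft and before month 12 is not a success of the randomized graft.
2. Have the blinded adjudicators apply this from a dated yes/no case report form field that does not reveal the arm.
3. Prespecify union regardless of further procedures as a supportive analysis, with the number of re-grafts per arm.
4. Do not build the failure rule from the exclusion criteria (such as exchange nailing, dynamization or stimulation). Those govern eligibility, and using them would bring more unblinded decisions into the endpoint. Report such procedures descriptively or in a sensitivity analysis.

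The DSMB's review of outcome definitions is a ready route.

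**Cost.** One revised definition, one form field and one supportive analysis. Union rates will be slightly lower, and the re-graft decision stays with surgeons who know the arm.

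The sponsor must also confirm whether the 65% and 85% are first-graft rates. If so, power stays at 80.7%. If not, the first-graft rate is (p − r)/(1 − r) and power must be restated:
- Both rates include 20% or 40% rescue: 81.25% v 56.25% or 75% v 41.67%, power 85.8% or 93.1%.
- Only the 85% includes it: 81.25% v 65% or 75% v 65%, power 68.6% or 46.2%.
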